## 1. OBJECTIVES

**1.1 Primary Objectives** – The primary objective is the evaluation of the effect of Aspirin as a chemopreventive agent for lung cancer. Particularly, the efficacy of Aspirin in reduction of size and number of CT-detected lung subsolid nodules will be evaluated in high-risk asymptomatic subjects currently undergoing CT screening programs at the European Institute of Oncology (EIO) and at MD Anderson Cancer Center (MDACC).

In addition, we will include subjects undergoing CT outside the context of a screening program with a subsolid nodule confirmed by pulmonary CT scan (qualifying scan).

The efficacy will be evaluated in a person-specific analysis.

**1.2 Secondary Objectives** – Secondary objective of the study will be the modulation of biological markers after treatment and the correlation of these findings with modification of lung nodules diameters. In particular we will evaluate the effect of Aspirin on a signature of serum microRNA correlated to subsolid nodules. Other secondary endpoints will be the per-lesion analysis including the evaluation of lung nodule density before and after treatment, the number and size of non target lesions including solid nodules and evaluation of response according to modified RECIST criteria. Additional biomarkers will include the modulation of ultrasensitive circulating hs-CRP, the evaluation of urinary cotinine as marker of tobacco exposure and investigation of the potential effect of aspirin according to its concentration, the measurement of urinary prostaglandin metabolites (PGEM) and leukotriene (LTE4), both normalized normalized to urinary creatinine concentration. Serum concentration of thromboxane B2 (TXB2) will be determined as a measure of compliance. We will also evaluate the tolerability of Aspirin at dose of 100 mg/day.

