### 3. SUMMARY OF STUDY PLAN

We will conduct a double-blind placebo-controlled phase IIb study in which participants will be randomized to receive either Aspirin (100 mg/day) or placebo for 12 months.

A total of 128 subjects will be accrued (randomized to drug or placebo); 64 per arm in a 3.5 year time period.

Participants will be men and women, current or former smokers, with undetermined subsolid lung nodules detected at low dose screening CT scan (without contrast medium) running at the EIO and MDACC. In addition, we will include subjects undergoing CT outside the context of a screening program, providing a subsolid nodule confirmation by a CT scan. Participants will be given 100 mg Aspirin daily or placebo for 12 months.

The primary endpoint will be the shrinkage of GGO and partially solid lung nodules after one-year treatment per-subject analysis.

Secondary endpoints will be the modulation of biological markers after treatment and the correlation of these findings with modification of lung nodules diameters. In particular we will evaluate the effect of Aspirin on a signature of serum miRNA correlated to subsolid nodules. Other secondary endpoints will be the per-lesion analysis including the evaluation of lung nodule density before and after treatment and the number and size of non target lesions. Additional biomarkers will include the modulation of hs-CRP, the evaluation of urinary cotinine as marker of tobacco exposure and investigation of the potential effect of aspirin according to its concentration, the measurement of urinary prostaglandin metabolites (PGEM) and urine leukotriene E4 (LTE4) both normalized to urinary creatinine concentration. Serum concentration of thromboxane B2 (TXB2) will be determined as a measure of compliance. We will also evaluate the tolerability of Aspirin at dose of 100 mg/day.

Complete physical exam and safety lab tests will be performed at 0, 6 and 12 months. Phone contact will occur at month 1, 3, 9 and 13 (i.e, one month after treatment completion).

Biomarkers: blood and urine will be collected at 0, 6 and 12 months

Lung lesions will be measured with a CT scan at 0 and 12 months. Both standard dose and low dose CT scans are allowed provided that the same procedure is used at both time points.

Duration of study will be five years: 3.5 years of accrual, one year of treatment and 0.5 year for biomarkers measurement.

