#### *miRNA*

The effectiveness of the miRNA serum protocol will be evaluated by comparing the sensitivity, specificity and accuracy of miRNA to identify patients with GGO or with partially solid nodules and to predict aspirin treatment response considering the LDCT screening protocol as the reference procedure.

The ultimate goal is to evaluate if miRNA analysis in the serum can represent a new non-invasive test to identify patients with GGO or with partially solid nodules and to predict treatment response to low-dose aspirin.

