#### *Additional biomarkers*

Additional biomarkers will include the modulation of hs-CRP as marker of inflammation, the evaluation of urinary cotinine as marker of tobacco exposure and investigation of the potential effect of aspirin according to its concentration, the measurement of urinary PGEM and LTE4 normalized to urinary creatinine concentration. Serum TXB2 will be determined as a measure of compliance. Results will be compared between the two treatment arms (aspirin and placebo).

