## **9. CORRELATIVE/SPECIAL STUDIES**

### **9.1 Rationale for Methodology Selection**

#### Blood

##### **miRNA analysis**

miRNA extraction and purification from serum (4.5 ml of blood) will be done accordingly to standard procedure. We will analyze approximately ~850 miRNAs using the TLDA qRT-PCR microfluidic cards (Applied Biosystems) and we will determine serum miRNA relative quantities using the  $\Delta\Delta Ct$ -method. Importantly, we will check the presence of hemolysis in all serum samples collected for miRNA screening. This will be done before the miRNA extraction by visual inspection and by measuring the absorbance at 414nm^45, and after analysis of the expression ratios of couples of miRNAs found by us and by others to be sensitive enough to reveal hidden hemolysis. In addition, we will introduce spike-in synthetic miRNAs to be used as standard references in every sample screened. This will allow us to control either the efficiency of the extraction procedure and of all the qRT-PCR reactions.

Data analysis will be performed using R software (<http://www.r-project.org/>) and SAS software (<http://www.sas.com/>) for correlation analysis with all other clinical, pathological and radiological parameters.

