## 13.5 Secondary Objectives, Endpoints, Analysis Plans

Generalized linear mixed models for longitudinal data will be used to compare the study groups using the standard general model  $y = X\beta + Zu + \epsilon$ , with  $y$  the response variable (e.g. secondary endpoint variable),  $X$  and  $\beta$  the design matrix and unknown parameters for the fixed effects and  $Z$  the design matrix for the random effects and  $u$  the random effects. Treatment arm (aspirin or placebo) and time visit (baseline, 6 and 12 months) will be considered fixed effects, smoking history and age at study entry random effects. Secondary endpoints include a per-lesion analysis by nodule type. Identity and logit link functions will be used for normal and binary data respectively. All tests will be two-sided and considered significant at the 5% level.

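### The planned correlation of marker change with nodule-diameter change does not specify conditioning on treatment arm, so a correlation run over both arms could reflect who received aspirin

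*Combined protocol and SAP*

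**What the plan says.** Section 1.2 sets as a secondary objective the "modulation of biological markers after treatment and the correlation of these findings with modification of lung nodules diameters". Section 3 repeats it: "Secondary endpoints will be the modulation of biological markers after treatment and the correlation of these findings with modification of lung nodules diameters".

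The method is named in one place. The miRNA part of Section 9.1 says R and SAS will be used "for correlation analysis with all other clinical, pathological and radiological parameters". It gives no estimator and does not mention arm. No such sentence exists for hs-CRP, PGEM or LTE4.

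Section 8.2 refers the reader to Section 13.5 for the analysis of secondary endpoints. There, "Generalized linear mixed models for longitudinal data will be used to compare the study groups", and "Treatment arm (aspirin or placebo) and time visit (baseline, 6 and 12 months) will be considered fixed effects", with smoking history and age as random effects. Section 8.2 also compares the additional biomarkers between arms, and gives as a goal for serum miRNA "to predict treatment response to low-dose aspirin".

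**The concern.** Arm is a possible common cause of both changes. The sample size assumes that aspirin shrinks nodules, and the markers were chosen partly because aspirin may act on them: Section 2.2 describes the anti-inflammatory action of this drug class as inhibition of prostaglandins, and PGEM is a prostaglandin metabolite. If aspirin moves both, aspirin participants cluster at one end of both scales and placebo participants at the other. A correlation over all participants is then non-zero even if, within each arm, the two changes are unrelated.

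The arm term in Section 13.5 does not settle this. That model has one response at a time and estimates the effect of arm on it. It has no marker term for a diameter outcome and no diameter term for a marker outcome.

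At stake is which markers are reported as following nodule shrinkage. A marker that only shows exposure to aspirin could be taken for one that tracks response, and this would happen in the scenario the trial hopes for. The primary test, the sample size, safety and the between-arm marker comparisons are not affected.

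**Working it through.** **Inputs from the documents.** Section 13.3: 64 per arm, difference 0.8 mm, SD 1.6 mm, two-sided 5%. Section 13.5: secondary tests two-sided at 5%.

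**Assumed.** The shift of the marker by aspirin, dm, in within-arm SD units, shown as a range because no document gives one. Also normal data, equal variances in the arms and no dropout.

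**The plan's own figure.** Standardised nodule effect dn = 0.8/1.6 = 0.5. The normal formula gives 2 × (1.96 + 0.842)² / 0.5² = 62.8, so 63 per arm. The exact t-test gives 63.8, so 64 per arm and 128 in all, with power 0.801. The stated sample size is reproduced. The documents give no figure for the correlation.

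**Correlation induced by arm.** With 1:1 allocation, an arm shift of d SD adds d²/4 to a variance, and two shifts add dm·dn/4 to the covariance. With within-arm correlation ρ, the pooled correlation is

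r = (ρ + dm·dn/4) / √[(1 + dm²/4)(1 + dn²/4)].

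With ρ = 0, dn = 0.5 and dm = 2: r = 0.25 / √(2 × 1.0625) = 0.171.

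The critical |r| for 128 participants is 1.979 / √(126 + 1.979²) = 0.174. As dm grows without limit, r approaches 0.25 / √1.0625 = 0.243.

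**False-positive rates**, by simulation (20,000 trials per setting, ρ = 0), comparing the pooled Pearson test (126 df) with the arm-adjusted partial correlation (125 df):

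| Nodule effect dn | Marker shift dm | Pooled r | Pooled test rejects | Adjusted test rejects |
|---|---|---|---|---|
| 0.5 (planned) | 0.5 | 0.06 | 10% | 5% |
| 0.5 | 1 | 0.11 | 23% | 5% |
| 0.5 | 2 | 0.17 | about 50% | 5% |
| 0.5 | 3 | 0.20 | 64% | 5% |
| 0.25 (half) | 0.5 | 0.03 | 6% | 5% |
| 0.25 | 2 | 0.09 | 17% | 5% |
| 0.25 | 3 | 0.10 | 21% | 5% |
| 0 | any from 0.2 to 5 | 0 | 5% | 5% |

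**If aspirin has no effect on nodules.** The pooled test is then valid, but the arm shift adds marker variance unrelated to the nodules. With ρ = 0.25 and dn = 0, the pooled r falls to 0.25/√2 = 0.177 at dm = 2 and 0.25/√3.25 = 0.139 at dm = 3. Simulated power is then about 51% and 35%, against about 81% with adjustment.

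**The case against.** The strongest reply is that the documents nowhere prescribe a pooled correlation. Sections 1.2 and 3 state an objective and not a test, Section 9.1 names software, and the only model given for secondary objectives contains arm. This stands in part. A reader might infer that the plan has chosen to ignore arm; it has not, it is silent. But the Section 13.5 model cannot produce the marker-diameter association, so its arm term does not fill the gap. The choice between pooled, within-arm and adjusted analysis is left open, and it can change the answer.

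A reader might also infer that every marker moved by aspirin will appear to track nodules. That does not follow. The bias needs aspirin to change nodules too, which is the untested primary hypothesis, and it is small for a modest marker shift. The larger rates need shifts of 2 to 3 SD, for which the documents offer no basis in PGEM, LTE4, hs-CRP or miRNA. Section 2.2 says low-dose aspirin has little activity against COX-2 and that its anticancer mechanism is unclear. The marker described as reliably showing aspirin use is TXB2, which serves here as a compliance measure.

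Pooling could also hide a true association of opposite sign: with ρ = -0.25, dm = 2 and dn = 0.5, pooled power is about 4% against 81% adjusted. That is a single chosen setting in which the two terms of the numerator cancel exactly, and nothing in the documents suggests it.

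Finally, an arm-adjusted correlation with one common slope does not test prediction of response to aspirin. This is right, and the change below allows for it.

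**Conclusion.** The concern holds as a gap with a definite consequence: a stated secondary objective has no arm-conditioned method, and the plain reading of a correlation over 128 randomised participants is open to confounding by arm. Under the planned nodule effect and no association within arm, the false-positive rate of a pooled test runs from about 10% at an assumed 0.5 SD marker shift to 64% at 3 SD. It is about 21% at 3 SD if the nodule effect is half of that planned, and 5% if there is none. These figures rest on assumed marker shifts, normality, equal variances and no dropout.

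The documents do not support saying that the plan pools the arms, or that any marker aspirin moves will look like a response marker. The point should be corrected because the better method is nearly free, but it touches a secondary objective only.

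**What to change.** Add to Section 13.5, with references from Sections 1.2, 3 and 9.1:

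- The association of marker change with diameter change is estimated adjusted for treatment arm, either as a partial correlation or by regressing diameter change on marker change with arm and the randomisation strata as covariates.
- The correlation within each arm is reported alongside.
- Where the question is prediction of response to aspirin, as for miRNA in Section 8.2, the regression includes a marker-by-arm term.
- An unadjusted correlation over both arms is not used to claim that a marker tracks nodule response.

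The cost is one degree of freedom for arm (126 to 125), four more if the four binary stratification factors enter as main effects (121), and one for an interaction (120). No new data are needed.

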## 2. BACKGROUND

### 2.1 Lung cancer

Lung cancer is one of the most common cancers in humans and the annual incidence continues to grow. The burden caused by lung cancer is enormous worldwide and largely due to tobacco use. In Western countries smoke cessation campaigns and stricter regulations are beginning to multiply. This strategy will surely achieve good results in the future. However, there are still age and gender groups (the younger and women) who are at present more reluctant to avoid smoking, while the smoking epidemic is hitting the underdeveloped countries more and more alarmingly. In the meanwhile, new screening modalities are under evaluation: the most promising is currently spiral low-dose CT scan (ld-CT).

### 2.2 Aspirin

Aspirin, the first non steroidal anti-inflammatory drug (NSAID) identified, may have anti-cancer properties, especially for diseases whose etiology implicates the role of chronic inflammation, such as colorectal and lung cancer. The anti-inflammatory effect of NSAIDs operates through inhibition of prostaglandins via suppression of cyclooxygenase-1 (COX-1) and COX-2. The most convincing evidence of this effect is derived from several recently published meta-analyses of aspirin in the prevention of cardiovascular events which showed that daily aspirin reduced the incidence of colorectal cancer and several other cancers and reduced metastases. In 2011, Rothwell et al. pooled data from 8 double-blind randomized controlled trials of daily aspirin and analyzed the effect of aspirin on cancer mortality as secondary endpoints. The 20-year risk of death due to all cancers was consistently lower in the aspirin groups than in the control groups and the benefit increased with duration of treatment.

Lung cancer-specific mortality rates were reduced by 29% (95% CI, 11-42) in the aspirin group in the 20-year period after the trial commenced. No trend with dose (above 75 mg/day) was observed, but the effect on all cancers was more evident in adenocarcinomas and was present in both smokers and nonsmokers. Several further observational studies have been published. In a prospective cohort study, total NSAID use was associated with a small reduction in risk of lung cancer, which was strongest for adenocarcinoma in men, and in long-term former smokers. A suggestion of a protective effect of low-dose aspirin was seen in the Women's Health Study. A hospital-base case-control study found that lung cancer risk was significantly lower for aspirin users compared to non-users and prolonged duration of use was associated with reduced lung cancer risk. Risk reductions were observed in both sexes, but significant dose-response relationship were only seen among male participants.

Controversy remains regarding the most appropriate long-term daily dose of aspirin in the prevention setting. The mechanisms by which aspirin reduces the risk of cancer are not clear. COX-2 is thought to be the isoform most commonly implicated in carcinogenesis, but at the low doses (80-325 mg), aspirin has little activity against this isoform^8. Aspirin is, in fact, 170 fold less effective at inhibiting COX-2 than COX-1. Nonetheless, aspirin may suppress the expression of COX-2, and it may also have antineoplastic effects that are unrelated to cyclooxygenase. Since the 81-mg dose and the 325-mg dose appear to suppress colorectal prostaglandin levels to a similar extent, we could postulate that the two doses may have equivalent potency through COX-related mechanisms. The major risk of aspirin, as with other NSAIDs, is the risk of bleeding. Although the antiplatelet effects of aspirin likely contribute to an increase in the risk of bleeding, as highlighted by an increased risk of hemorrhagic stroke of 0.2 events per 1000 patient-years, the majority of the increased bleeding has a gastrointestinal tract etiology. The influence of aspirin on gastric prostaglandin levels is dosage-dependent, with almost 50% inhibition at just 30 mg/d, but maximal inhibition requires approximately 1300 mg/d. Consistent with these data, all conventional dosages of aspirin are associated with an increased bleeding risk. In a clinical trial in which 1,121 patients with a recent history of histologically documented adenomas were randomly assigned to receive placebo (372 patients), 81 mg of aspirin (377 patients), or 325 mg of aspirin (372 patients) daily, the risk of bleeding was not a substantial problem and the risk of death and serious bleeding were similar among the groups. In a case-control study of patients admitted with gastrointestinal bleeding, the odds ratio (OR) for admission with a bleeding ulcer was increased among aspirin users regardless of dosage. Treatment with a 75-mg/d dosage of aspirin was associated with an odds ratio of 2.3 for a bleeding ulcer (95% CI, 1.2-4.4), whereas 300 mg/d increased the OR to 3.9 (95% CI, 2.5-6.3).

### 2.3 Rationale

With the evolution of helical CT technology, CT screening for early detection of lung cancers is under evaluation in high risk individuals (former and current heavy smokers) with encouraging results. At the EIO, a single center screening trial recruited 5,202 high-risk volunteers (both current or former smokers) to undergo an annual multidetector low dose CT (ld-CT) for 5 or more years, beginning in 2004. The screening ld-CT, a non invasive test with low radiation exposure and no contrast medium, affords the opportunity to serially examine the peripheral lung for the first time, albeit with the limitation that small lesions cannot be biopsied and thus their identity remains unknown.

In September 2012, a new multicenter screening program has been launched at the EIO (Cosmos 2) with the aim of enrolling 10,000 high-risk individuals in 6 centers in Italy in a one-year period, with the goal of recruiting 5000 at the EIO. The Cosmos protocol requires once yearly low-dose CT for 5 years. One of the main objective of the study is the validation of a serum signature of 34 circulating microRNA able to predict with high sensitivity the presence of an asymptomatic lung cancer and to validate the Cosmos risk model on an independent cohort of high risk individuals to better select the target population for screening and the optimal screening interval. The population enrolled in the Cosmos 2 will represent the major source of potentially eligible subjects for the chemoprevention study.

In the meantime, two other screening programs are still ongoing at the EIO with annual ld-CT scans (Cosmos 1 and a pilot study) and they represent an additional source of potential participants.

Unfortunately, the high rate of benign nodules and issues of making a differential diagnosis are critical factors that currently hamper introduction of large-scale screening programs. Small pulmonary nodules are, in fact, a frequent finding in the subjects submitted to ld-CT for early detection of lung cancer and have no clinical implications. Our data have demonstrated an incidence of undetermined lung nodules in more than 50% of high risk individuals. The nature of these nodules remained uncertain but it is reasonable that some of them could represent precancerous lesions. In particular, literature suggests that ground glass opacities (GGO), as compared with solid nodules, can represent either localized bronchioloalveolar carcinoma without foci of active fibroblastic proliferation or atypical adenomatous hyperplasia which is a known putative adenocarcinoma precursor lesion. The possibility to measure the nodule density in GGO lesions is an additional tool to monitor these preneoplastic lesions.

The actual identity of ld-CT detected GGO cannot be ascertained without histologic analysis, but this is the category of nodule that is most likely to represent atypical alveolar hyperplasia, the putative precursor of pulmonary adenocarcinoma. Kim et al. reported that of 53 persistent GGO in 49 patients who underwent resection, 68% proved to be bronchoalveolar carcinoma, 7.5% were adenocarcinoma with predominant bronchoalveolar components, 6% were atypical adenomatous hyperplasia, and 19% were nonspecific fibrosis or organizing pneumonia. Similarly, Ohtsuka et al. reported that of 26 patients who underwent resection, bronchoalveolar carcinoma was diagnosed in 10 patients (38%), atypical adenomatous hyperplasia was diagnosed in 15 patients (58%), and focal scar was seen in 1 patient (4%). Although criteria such as size, the presence of air bronchograms, and nodule sphericity on CT scan have been used to differentiate carcinomas from atypical alveolar hyperplasia, histological analysis remains the gold standard for definitive categorization of nodules and there continues to be debate regarding the overlap between small bronchoalveolar carcinomas and atypical alveolar hyperplasia. Since resected nodules represent lesions that are suspicious enough to merit surgery, it is possible and even likely that the smaller nodules identified in the context of our ld-CT screening study represent less advanced neoplasia than described in the above cited studies as well as non-neoplastic etiologies.

In 2010 we published the results of the Budesonide trial (MDA05-5-01), a randomized phase IIb study that evaluated the role of inhaled Budesonide in the shrinkage of CT detected undetermined lung nodules. The study showed an effect of the treatment only on non solid nodules and a trend in partially solid nodules. A 5-year follow up of the nodules with annual low dose CTs showed that the effect of treatment was maintained years after treatment and was significant for non solid and partially solid nodules (unpublished data). Specifically, after 60 months the mean reduction of maximum diameter in the treated arm were 2.65 mm and 0.69 mm in the non-solid and partially solid lesions, respectively.

We concluded that screen-detected non solid and partially solid nodules represent a good target to test chemopreventive agents and that the role of Budesonide deserves further investigation.

The University of Texas MD Anderson Cancer Center launched its Lung Cancer Screening Program in 2011. To date, nearly 800 patients have been screened averaging approximately 20-30 screened patients per month. An additional resource for screening CTs is the active protocol entitled "*Biospecimen Banking and Biomarker Validation for Lung Cancer Early Detection in Cohort Receiving Low Dose Helical Computed Tomography Screening*" which has 194 patients currently enrolled. Although literature indicates the frequency of eligible lesions is approximately 30%, MDACC's experience is slightly less at 10% (2-3 patients per month) identified by low dose screening CT scan. From this population, it is anticipated the Lung Cancer Screening program may enroll less than 1 eligible patient per month after evaluation of other eligibility criteria. However, with the inclusion of lesions identified by diagnostic CT scan, MDACC's large cancer survivor population offers a larger pool of potentially eligible patients undergoing CTs for surveillance.

Based on the recent knowledge on the chemopreventive effect of Aspirin on lung cancer, we intend to evaluate the effect of low dose Aspirin (100 mg/day) on non solid and partially solid nodules identified in high risk volunteers submitted to annual low dose CTs among the ongoing screening programs at EIO and MDACC.

In addition, we will include subjects undergoing CT outside the context of a screening program with a subsolid nodule confirmed by pulmonary CT scan.

